- We predict that the shorter interval of follow-up (1 year) will allow the diagnosis of lesions in a less advanced stage (more outcome 1 – dysplasia - and lower or inexistent outcome 2 - cancer);
- We anticipate that 1% of patients at risk per year will develop one of the outcomes (6% at the end of the 6-year follow-up) and that most of outcomes 2 (cancer) will be reached in the longer period of follow-up (3 year) for a 6-year total of 1% outcome 2 in the 1-year follow-up group (and 5% outcome 1) and 5% in the 3-year follow-up group (and 1% outcome 1);
- For showing this 4% incidence difference between the two groups (4% more incidence of outcome 2 in the 3-year follow-up group) at the end of follow-up (6 years) with an alpha level of 0.05 and a power of 90% we calculate that at least 760 patients will have to be randomized (380 per group of follow-up);
- Predicting 20% of lost to follow-up and/or necessity to anticipate endoscopy in some patients (because of symptoms/clinical reasons) we calculate that additional 152 patients will have to be randomized for a **total of 912 patients (456 per group of follow-up)**;
- We predict participation of at least 15 centers and, so, **each center must include at least 62 patients in the randomization**;
- Since inclusion of the patients in the randomization trial will only be known after an initial endoscopic and histologic evaluation, and predicting that only 20-25% of the patients will have criteria for inclusion in SUPREME I **each center must include at least 300 patients in the study (these patients will be included in SUPREME II and III)**.

Flowchart (SUPREME I, II AND III)

DISCUSSION/EXPECTED RESULTS

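### The 5% cancer figure for the 3-year arm does not fit the other planning assumptions: at a steady 1% a year it is at most about 4.3%, and the stated 90% power falls to about 80-85%

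*Protocol*

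**What the plan says.** All the planning figures stand in the protocol, section Sample size calculation (SUPREME I).

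- Event rate: "We anticipate that 1% of patients at risk per year will develop one of the outcomes (6% at the end of the 6-year follow-up". No difference between the arms is stated.
- Split by arm: "1% outcome 2 in the 1-year follow-up group (and 5% outcome 1) and 5% in the 3-year follow-up group (and 1% outcome 1". Each arm totals 6%.
- Effect to be shown: "4% more incidence of outcome 2 in the 3-year follow-up group".
- Size: "with an alpha level of 0.05 and a power of 90% we calculate that at least 760 patients will have to be randomized", that is 380 per arm, raised to 912 (456 per arm) for 20% losses or endoscopies brought forward.

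Three other parts of the protocol bear on these figures. The section on inclusion and randomization sets the intervals at 12-16 months and 32-40 months. The baseline endoscopy section excludes patients with a suspected superficial lesion or dysplasia. The End of study section closes a patient's follow-up at the first outcome, so each patient counts once, as dysplasia or as cancer. No natural-history model or source is given for the 1%/5% split.

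**The concern.** The two arms are supposed to produce the same number of lesions and to differ only in how far those lesions have advanced when found. But the nominal yearly schedule (years 1 to 6) contains both examinations of the 3-year schedule (years 3 and 6). A lesion that the yearly arm first finds as dysplasia at year 3 or 6 would be found by the 3-year arm at the same examination and the same stage. That sets a floor under dysplasia in the 3-year arm, and the planned 1% appears to lie below it.

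The randomised comparison serves primary aim 2, the choice of follow-up interval, and its size rests entirely on 1% v 5%. If 5% is out of reach under the plan's other assumptions, the trial is described as better powered than it is, and a non-significant result would be read against too favourable a figure.

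**Working it through.** **Inputs** (sample size section unless noted): total outcomes 6% in each arm at 1% a year; cancer 1% and dysplasia 5% in the yearly arm; cancer 5% and dysplasia 1% in the 3-year arm; alpha 0.05, taken as two-sided; power 90%; 380 per arm before losses, 456 after; intervals 12-16 and 32-40 months (inclusion and randomization section).

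**Step 1. Reproduce the 760.** The formula is the two-proportion one with pooled variance under the null, two-sided and without continuity correction:

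n = [1.960·√(2p̄(1−p̄)) + 1.282·√(p₁(1−p₁) + p₂(1−p₂))]² / (p₂−p₁)²

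With p₁ = 0.01, p₂ = 0.05 and p̄ = 0.03, n = 380.1, or 381 per arm when rounded up. Power at 380 per arm is 90.0%. The stated figure is reproduced, so the formula is not at fault.

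**Step 2. Floor on dysplasia in the 3-year arm.** With steady onset and the same cancer share each year, the yearly arm's 5% dysplasia is spread evenly over six examinations. The part first found at years 3 and 6 is 5% × 2/6 = 1.67% of patients. The 3-year arm finds the same lesions at the same examinations, so its dysplasia is at least 1.67%, against the planned 1%.

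**Step 3. Ceiling on cancer in the 3-year arm.** 6% − 1.67% = 4.33%, so the largest difference is 3.33 points. The same result by lesion age: one third of the lesions (2% of patients) are at most one year old and carry the yearly arm's share of 1/6, giving 0.33%. If every older lesion (4% of patients) is cancer, the sum is 4.33%. To reach 5%, the older lesions would have to supply 4.67 points out of 4, or 117%.

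**Step 4. Visit windows.** In general the ceiling is 6% × [1 − (I₁/I₃) × 5/6], where I₁ and I₃ are the two intervals.

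- 12 and 40 months: 6% × 0.75 = 4.5%.
- 12 and 36 months: 4.33%.
- 16 and 32 months: 6% × 0.583 = 3.5%.

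**Step 5. Power against 1% in the yearly arm**, by the formula of Step 1, 380 per arm:

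| Cancer in 3-year arm | Basis | Power |
|---|---|---|
| 5% | as planned | 90.0% |
| 4.5% | ceiling, 12 v 40 months | 84.0% |
| 4.33% | ceiling, 12 v 36 months | 81.5% |
| 3.5% | ceiling, 16 v 32 months | 64.2% |
| 3.0% | illustrative: cancer share rising linearly with lesion age | 50.4% |
| 2.4% | illustrative: constant progression hazard | 32.1% |

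Both illustrative rows are tuned to the 1% in the yearly arm. In the linear case the share at age a years is a/3; it averages 1/6 over one year and 1/2 over three, and 6% × 1/2 = 3.0%. In the constant-hazard case the rate is 0.376 a year, the three-year average is 0.401, and 6% × 0.401 = 2.4%.

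At 4.33%, the 365 per arm left after losses (456 × 0.8 = 364.8) give 79.9%. Exact enumeration of the uncorrected chi-square test gives 84.7% with 380 and 83.1% with 365. On that same test 1% v 5% has 93.0% with 380, so the fall is about 8 points by either method. By the formula, 90% power at 4.33% needs 489 per arm before losses.

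**The case against.** A reader might infer that the planning figures contradict each other outright, so that 5% cancer and 90% power are impossible. The documents do not support that. Each split adds to 6%, the difference is 4 points and the 760 reproduces. The conflict needs an assumption that the protocol does not write down: a cancer share in the yearly arm that is the same every year. Without it, the ceiling is 4% plus whatever part of the yearly arm's 1% cancer falls at years 3 and 6, which can be as much as 5.0%.

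A second route runs through lesions present but unseen at baseline. The baseline exclusion removes only what was seen, the Introduction accepts that random biopsies can miss important changes, and outcomes are assigned at diagnosis. Speaking of patients who will develop an outcome therefore does not clearly rule out carry-over. If a share q of all outcomes was missed at baseline, the ceiling becomes 6% × (13/18 + q/3), which equals 5% at q = 1/3.

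The power loss can also be overdrawn. With all 456 per arm and no losses, power at 4.33% is 87.9% by the formula and 90.9% by exact chi-square. The 20% allowance includes endoscopies brought forward, and those patients may still contribute outcomes, so 365 is a lower limit.

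All of this stands, and it rules out the absolute reading. It does not rescue 5% as an expected value. The first route needs every yearly-arm cancer at years 3 and 6 and every lesion from years 1, 2, 4 and 5 to be cancer in the 3-year arm. The second needs a third of all outcomes missed at baseline, all still dysplasia at 12 months and all cancer at 36. The protocol states neither. Nor is the 4.33% ceiling a contrived case that understates the arm: any conversion times averaging 10 months and never above 12 produce it, and it already counts every lesion older than a year as cancer.

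**Conclusion.** The point holds under the plain reading of the plan: steady onset at 1% a year, 6% in both arms, 1% cancer in the yearly arm and a constant cancer share by year. On those assumptions the 3-year arm has at most about 4.3% cancer (3.5% to 4.5% across the visit windows), and the difference is at most about 3.3 points at nominal intervals. Power for the planned numbers, allowing for the predicted losses, is then about 80-85% at best, depending on the test. With slower progression it is much lower: about 50% at 3.0% cancer and 30-32% at 2.4%. Those two cases are illustrations, not estimates from the documents.

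The planned 5% is thus a limiting value used as an expected one, with the assumption that would support it left unstated. This is an error in the planning set as written, but not a contradiction under every reading.

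**What to change.** In the sample size section, do one of two things.

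- Replace 1%/5% with a jointly possible set: keep 1% a year and 1% cancer in the yearly arm, and put the 3-year arm at no more than about 4.3%.
- Or keep 5% and state what supports it: the assumed share of lesions missed at baseline, or the assumed change of the cancer share over the years, with a reason.

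Under the steady-rate assumptions, restate the power of the planned 760/912 as about 80-85% at best, name the test, and add a short table of power for about 2.4% to 4.3% cancer in the 3-year arm.

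The cost is a rewritten paragraph and a less favourable stated power. The number randomised need not change.

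### The 20% loss allowance is added to 760 rather than divided out: if all 20% leave the analysis, 912 randomised gives about 89% power, not 90% (minor)

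*Protocol*

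**What the plan says.** All the figures are in the protocol, section Sample size calculation (SUPREME I).

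- **Before loss.** Cancer (outcome 2) is expected at 6 years in 1% of the yearly group and 5% of the three-yearly group. With alpha 0.05 and 90% power, "we calculate that at least 760 patients will have to be randomized (380 per group of follow-up".
- **Loss.** "Predicting 20% of lost to follow-up and/or necessity to anticipate endoscopy in some patients", the section adds 152 patients: "we calculate that additional 152 patients will have to be randomized".
- **Total.** The target is given as a "total of 912 patients (456 per group of follow-up".
- **Centres.** "We predict participation of at least 15 centers", and from this "each center must include at least 62 patients in the randomization".
- **Screening.** "predicting that only 20-25% of the patients will have criteria for inclusion in SUPREME I", the section concludes that "each center must include at least 300 patients in the study".

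**The concern.** An allowance for loss should leave the required number after the loss has happened. The predicted fraction applies to everyone randomised, so the required number has to be divided by the fraction retained. The section instead takes 20% of the required number and adds it, which replaces fewer patients than the prediction removes.

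At stake is whether the stated total, loss and power agree with one another. If the whole 20% leaves the analysis, they do not. The practical consequence is that the retention margin over six years of follow-up is narrower than the section suggests.

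**Working it through.** **Inputs** (all from the sample size section): outcome 2 rates p1 = 0.01 and p2 = 0.05; alpha 0.05; power 90%; equal groups; 760 before loss; 20% loss; 912 in total; at least 15 centres; centre minima of 62 randomised and 300 included; 20–25% eligible.

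**Assumptions.** The test is two-sided; the protocol does not state this, but a two-sided test without continuity correction is the variant that reproduces 760. Loss is equal in both groups. All eligible patients are randomised, as the protocol summary says.

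**1. Reproduce 760.** Pooled two-proportion formula, mean rate 0.03:

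n per group = [1.960 × √(2 × 0.03 × 0.97) + 1.282 × √(0.01 × 0.99 + 0.05 × 0.95)]² / 0.04²
= (0.4728 + 0.3070)² / 0.0016 = 380.1

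This agrees with the stated 380 per group.

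**2. Reproduce 912.** 760 × 0.20 = 152, and 760 + 152 = 912.

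**3. Apply the predicted loss to 912.**

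- Lost: 912 × 0.20 = 182.4, which is 30.4 more than the 152 added.
- Remaining: 912 × 0.80 = 729.6, about 365 per group, against the 760 required.
- Matching total: 760 / 0.80 = 950, which is 38 more than 912 (38/912 = 4.2%).
- Loss that 912 can absorb: 1 − 760/912 = 16.7%.

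**4. Power by number remaining.** Power = Φ{[0.04 × √n − 0.4728] / √0.0574}, with n per group.

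| Randomised | Loss | Remaining | Power |
|---|---|---|---|
| 912 | 20% | 729.6 | 88.8% |
| 912 | 16.7% | 760 | 90.0% |
| 912 | 15% | 775.2 | 90.5% |
| 930 (15 × 62) | 20% | 744 | 89.4% |
| 950 | 20% | 760 | 90.0% |

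**5. The screening minimum.** 15 × 300 = 4,500 included. With 20% loss after randomisation:

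| Eligible | Randomised | Remaining | Power |
|---|---|---|---|
| 20% | 900 | 720 | 88.4% |
| 21.1% | 950 | 760 | 90.0% |
| 22.5% | about 1,012 | 810 | 91.7% |
| 25% | 1,125 | 900 | 94.2% |

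At 20% eligible, the separate minimum of 62 would raise 900 to 930.

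**6. Other methods.** Going from 380 to about 365 per group changes power as follows:

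| Method | 380 per group | About 365 per group |
|---|---|---|
| Unpooled normal approximation | 90.2% | 89.0% |
| Fisher's exact test | 90.0% | 88.5% |
| Continuity-corrected approximation | 85.7% | 84.1% |
| Uncorrected chi-squared test, by enumeration | 93.0% | 91.9% |

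The level depends on the method. The drop is between 1.1 and 1.6 points in every case.

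**The case against.** The strongest objection is that the 20% is not all loss. It includes patients whose endoscopy is brought forward. They are still examined, and nothing in the protocol removes them from the analysis. If about 30 of the 182 (3.3 of the 20 points) are retained, 760 remain and the 90% stands. This is right, and it is why the conclusion is conditional. It does not rescue the arithmetic, because the section itself counts these patients in the 20% it sets out to replace, and 152 does not replace 20% of 912. The break-even also assumes that retained patients show the full 1% against 5% contrast. An earlier endoscopy in the three-yearly group moves those patients towards the shorter interval and could shrink that contrast.

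A second objection is that the centre minima cover the gap. They narrow it: 930 is 0.6 points short, and 950 is reached at 21.1% eligibility, which leaves (25 − 21.1)/5, about 78%, of the stated eligibility range on the safe side. But 930 is still below 950. The protocol's Setting and study design section also grants participation to centres completing 100 patients, 25 of them randomised, which is well below 62 and 300. The reassurance holds only if the higher minima are enforced.

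A third objection is that the size is trivial beside the uncertainty in the event rates. With 380 per group, a three-yearly rate of 4.8% rather than 5% gives 87.9% power, and 4.5% gives 84.0%. Likewise, the enumerated chi-squared test keeps more than 90% power at 365 per group. Both points stand, and they are why this is minor. They do not make the printed figures consistent.

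**Conclusion.** The concern holds and is minor. On the calculation that yields 760, randomising 912 and losing 20% leaves about 730 patients and 88.8% power, 1.2 points below the stated 90%. If every one of 15 centres meets both minima in the sample size section, the shortfall is at most about 0.6 points, and arises only when eligibility is below 21.1%.

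This rests on a two-sided test, equal loss in the two groups, and the whole 20% leaving the analysis. If no more than 16.7% leave and the rest show the assumed contrast, 912 delivers 90%. The design is not threatened; the stated total simply does not carry the stated loss at the stated power.

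**What to change.** In Sample size calculation (SUPREME I), keep 912 and restate what it delivers: if the full 20% leave the analysis, 912 randomised leaves about 730 and gives about 89% power; 90% power holds up to 16.7% loss; the total matching 90% power at 20% loss is 760/0.80 = 950. It would help to say in the same place whether patients with an earlier endoscopy stay in the analysis, since that decides which figure applies.

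This costs wording only, with no new patients, visits or data. If the sponsor prefers to adopt 950, that is 38 more patients, or 950/15 = 63.3 per centre, so the centre minimum would rise from 62 to 64.
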